Protocol Template Guidance

For Submissions to CORIHS

TITLE: Aromatherapy for management of back pain in the Emergency Department

INVESTIGATORS: [name] MD / [name] MD / [name] BS
Department of Emergency Medicine

A. SPECIFIC AIMS

This study aims to research the use of aromatherapy for pain control in the emergency department, specifically, acute back pain. Aromatherapy, particularly Rose Essential Oil (Rosa damascena) has been studied in recent literature and shown to be effective versus placebos for the control of acute pain with lasting effects during burn dressing changes and post-operative pain management. These studies have been small and specific to discrete clinical conditions. Their evidence supports the use of aromatherapy for acute pain control with additional patient satisfaction benefit, but they are not yet externally validated to more common conditions facing emergency medicine physicians. We chose to study acute isolated back pain and sciatica presenting to the emergency department and the use of Rosa damascena essential oil versus a control of Almond Oil for the treatment of isolated back pain and sciatica. We will investigate the use of aromatherapy in pain management by measuring and comparing pre- and post-treatment pain levels using a 100 mm visual analog scale (VAS) for pain. A significant reduction in pain by 13 mm on the VAS has been previously demonstrated as the minimal clinically important difference for treatment of pain (). Our primary endpoint will be the evaluation of significant change in VAS score greater than 13 mm between both groups immediately following a 30 minute blinded aromatherapy treatment and again 30 minutes later. Our secondary measures include patient satisfaction, need to rescue medication (its type and dose), and subjective changes in pain.

B. Background and Significance

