Aromatherapy has been hypothesized to be an effective management strategy for acute pain control. Its use has been recently demonstrated in Iran, using Rosa damascene (Damask Rose) essential oil. Rosa damascene is believed to possess anti-anxiolytic, sedative, anticonvulsive, and analgesic effect on the CNS when delivered through the olfactory system (Mohebitabar et al. 2016). This theory is believed to be in part due to the lateral gate theory of pain control and a stimulant's ability to inhibit transmission of stimuli through pain fibers. However, while any olfactory stimulant might be hypothesized to do just that, only Rosa damascena has been shown to produce significant reduction in pain on the VAS as well as patient satisfaction when compared to scented placebos like Almond Oil. Rosa damascene has been shown to improve pain control during dressing changes of second- and third-degree burns (Bikmoradi et al 2016). It has also been shown effective and equal to NSAID treatment of immediate post-operative pain in children (Marofi et al. 2015). It may be an affordable and easy-to-use modality for pain control in the emergency department. Its prior studies are small in sample size and carry little external validity that could be applied to an American Emergency Department population. We aim to assess whether aromatherapy using Rosa Damascena is reproducible in the emergency department for control of isolated and acute back pain, two common painful conditions seen with poor evidence for proper pain control. Validity of Rosa damascene aromatherapy in acute back pain and sciatica may open new doors of pain control to be researched in the emergency department and will further characterize the use of aromatherapy in modern medicine.

C. Preliminary Studies

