Isolated acute back pain (less than 2 weeks duration) and sciatica are common complaints to the emergency department requiring acute pain management with often chronic follow-up. Their abundance in the ED as well as poorly defined treatment recommendations make them an excellent candidate to study the use of aromatherapy in the emergency department. We will replicate the Rosa damascena trials referenced above in similar protocols, patients will be recruited if they fit the attached inclusion criteria and do not meet exclusion criteria. Patients will be treated with either Almond Oil extract or Rosa damascena extract, and both the investigator and patient will be blinded to the control arm. A VAS pain scale will be recorded before treatment, after 30 minutes of treatment, and after a following 2nd 30 minutes. Patients will additionally be asked about their satisfaction and subjective changes in pain, they will be blinded to their prior VAS line placements for proper evaluation of objective pain level changes. Demographics thought to contribute to the sensation of pain, expression of pain, and response to pain treatment will additionally be collected without entangling PHI. Finally, the use of rescue medication such as NSAIDs or Narcotics at the treating physician's discretion will be recorded as an indicator of treatment failure and complication. Pain will be qualified in its type, locations, duration, immediate episodes prior to presentation, and prior remote episodes in the patient's lifetime health history. Pain will also be quantified by attempted at-home treatments prior to presentation.

Research Site

The entirety of this prospective clinical trial will be conducted at the Stony Brook Hospital Emergency Department, an ED with over 80,000 annual visits.

Study Sample

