Patients will be recruited into this study by an investigator in the Stony Brook Emergency Department. A sample size was calculated to be 30 patients for each treatment arm based on a power of 0.80, desired p value below 0.05, and 95% confidence intervals with the anticipated possibility of patient loss or desire to withdraw during treatment. Patients will be approached for recruitment after an attending or resident physician has seen them and does not anticipate immediate need for narcotic pain medication, immediate imaging, or immediate threats to life or limb. Patients will be included by the attached inclusion and exclusion criteria. Double-blinding will be ensured by block randomization of each treatment arm, performed outside of the emergency department. In the Emergency Department Research Offices, the two treatment arms will be allocated into identical, individual vessels with only a codified label applied to each. Using block randomization, 30 treatments will be distributed to each arm in secret by a clinical research assistant or [name]. Each treatment will be codified individually and recorded in secrecy and kept from the investigators, [name] and [name]. Randomization will then arrange the total 60 treatments in longitudinal order for sequential random treatments to be selected as each patient is recruited.

Screening

Patients will be approached in private and the name, title, and role of the investigator explained after asking permission to speak with the patient. The patient will be told that we are conducting a clinical research trial for the treatment of acute back pain and sciatica. Aromatherapy will be explained as the treatment of interest and a modality that has been tested and proven in other types of pain. The use of Almond products and Rose products will be briefly discussed with the patients. Patient's will be asked about any allergies and then asked specifically about allergies to Almonds, Roses, perfume, and ibuprofen. Patient will be informed that speaking with the investigator is entirely optional, as is participating in the study, as there may be no direct benefit to them despite disclosure of their private information to the investigator. An Inclusion and Exclusion form will be reviewed with the patient and

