their chart, noting their sequential patient number in this study as the only de-identified patient ID. No PMI will be collected; no MRN, address, phone number, emails, name, SSN, DOB, chief complaint, PMH, PSH, or medications will be recorded. The risks and benefits will be explained to the patient including risk of allergy, risk of no change in pain, benefit of pain improvement, and benefit of contribution to medical research. The consent form will be reviewed in full and any questions answered. Those patients interested in participating and able to grant consent will do so.

Procedures

Rosa damascena 40% and Almond Oil 40% kept outside of the ED will be prepared each day and dispersed into identical vessels with randomized identification numbers. The coded numbers and their respective modality will be recorded by an investigator not involved in delivery and kept secured. Patients will be chosen into random treatment arms by block randomization and their coded treatment recorded on the patient data sheet. Patients will be given 4 drops of either modality (40%) on a cotton ball kept between 20 and 30 cm from their face for 30 minutes.

With regards to study blinding, the treatments will be randomly assigned and the patients will not be told which treatment they are receiving. The patients will be aware that the study involves Rose and Almond scents and will likely be able to identify the scent used in their treatment. However, at the end of the study procedures, an independent observer will assess the patient's pain after the aromatherapy has been removed from the room, and will not be aware of which patients received which treatment.

E. Statistics

VAS differences immediately after treatment and 30-minutes following will be aggregated from their respective 100 mm VAS for pain and the change calculated for each patient. One-tailed paired t-Tests will be then conducted on the means after standard deviation is calculated and compared between treatment and control groups. A chi-squared test will then be applied between both groups for analysis of significant differences in patient satisfaction and subjective reports of pre- and post-treatment pain. The use of rescue medications by type and dosage will be measured as a percentage of each group and compared via t-Test between both groups.

F. Funding

Rosa damascene and Almond Oil are affordable and readily available over-the-counter. This trial requires no significant funding to be conducted.

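### The plan says double-blinding is ensured, but its measures conceal allocation without masking odour, and it expects patients to recognise their scent

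*Combined protocol and SAP*

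**What the plan says.** Four parts of the combined protocol and SAP describe blinding.

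- **A. Specific Aims** sets up the comparison as "the use of Rosa damascena essential oil versus a control of Almond Oil". It places the primary readings "immediately following a 30 minute blinded aromatherapy treatment and again 30 minutes later".
- **D. Rationale and Overview** says that "both the investigator and patient will be blinded to the control arm". It says of patients that "they will be blinded to their prior VAS line placements", which indicates that they mark the scale themselves. VAS readings are taken before treatment, after 30 minutes of treatment, and 30 minutes after that.
- **D. Study Sample** states: "Double-blinding will be ensured by block randomization of each treatment arm". The oils go into "identical, individual vessels with only a codified label applied to each", and the code list is withheld from the investigators.
- **D. Procedures** says that patients are not told their assignment, but that they know both scents are in use and "will likely be able to identify the scent used in their treatment". It then adds an independent observer, unaware of assignment, who assesses pain when the procedures end and the oil has left the room.

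Two further statements bear on what patients may infer. The Screening text has staff present aromatherapy in general as the treatment of interest and mention almond and rose products together, without naming either as the control. Background and Significance describes earlier rose-oil results "when compared to scented placebos like Almond Oil", so the comparator is itself scented.

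**The concern.** Double-blinding cannot be ensured by a randomization method when the treatment is a smell and the plan expects the recipient to recognise it. The primary outcome is a subjective pain score, and satisfaction and reported change in pain are also patient-reported. If the trial is published as double-blind on the strength of Specific Aims, Rationale and Overview, and Study Sample, readers will take expectation to have been ruled out as an explanation for a difference. The Procedures text does not support that. The observer is the only remedy offered, so it matters what the observer can protect and at which readings.

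**Working it through.** No arithmetic settles this point, so the statements are set side by side.

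**1. What the measures achieve.** Block randomization makes the sequence hard to predict. Identical coded vessels hide the label. Both serve allocation concealment. Neither acts on odour, and the oil is delivered by smell: 4 drops on a cotton ball, 20 to 30 cm from the face, for 30 minutes.

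**2. Who is masked to what.**

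| Person | Told the assignment? | Could recognise the oil? | Would that reveal the arm? |
|---|---|---|---|
| Patient | No (Procedures) | Likely, by the plan's own statement | Only if the patient knows or infers which oil is under test; the Screening text does not say, and the consent form is not shown |
| Investigator delivering treatment | No; codes are withheld (Study Sample, Procedures) | Yes, if close enough to smell it; the text does not say who places the cotton ball or stays in the room | Yes, because Specific Aims names almond oil as the control |
| Independent observer | No (Procedures) | Less likely, as the oil has been removed; residual odour is possible | Yes, if recognised, where the observer knows the protocol |

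The patient row leaves room for a form of blinding: knowing the scent but not its role. The investigator row does not, for anyone who smells the oil. Double-blinding is therefore not ensured, whatever patients infer.

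**3. Who produces the rating.** The wording on patients' earlier VAS marks implies that the patient draws the line. This is an inference, as the plan does not say so outright. On that basis the observer can prevent staff from steering the answer, but cannot blind the person giving it.

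**4. Which readings the observer covers.** There are two post-treatment readings, at 30 and 60 minutes from the start of treatment. The observer's attendance is described once. The end of the procedures could mean the end of the whole visit, which covers only the 60-minute reading. It could also mean the end of the inhalation, which would allow both. The text does not decide between them.

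**5. Whether a bias can be sized.** A bias between arms needs patients in one arm to expect more relief than patients in the other. The documents give no SD, no rate of scent recognition and no estimate of how expectation shifts the VAS. A false-positive rate would rest entirely on invented inputs, so none is given.

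**The case against.** The strongest reply is that the plan is candid. Procedures raises the scent problem under the subject of blinding and adds an observer in response. Both arms receive a scent, the Screening text treats the oils symmetrically, and codes are withheld from investigators. If blinded means not knowing which oil is the active one, patients may well be blinded.

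Much of this stands, and it rules out three stronger readings.

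- A reader might infer that the comparison is **biased towards rose**. The documents do not support that. It would require patients to infer that rose is the oil under test, and nothing shown tells them so.
- A reader might infer that **staff who know the assignment collect one of the primary readings**. The codes are kept from the investigators without limit to one reading. What is missing is a statement of who collects the 30-minute VAS and whether that person has smelled the oil.
- A reader might infer that the **30-minute reading is definitely outside the observer's cover**. The wording is ambiguous and may have been meant to include it.

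The candour does not rescue the label. The admission in Procedures is what makes the unqualified claim in Study Sample untenable, and the other blinding statements were left unreconciled with it. Nor does patient ignorance of the oils' roles help an investigator who can smell almond and knows it is the control.

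**Conclusion.** The concern holds as a mismatch between label and design. Allocation is concealed and nobody in contact with the patient is told the assignment, but odour is not masked, so the claim that double-blinding is ensured is wrong as written. The independent observer reduces staff influence without blinding a patient-marked score, and the observer's cover of the two post-treatment readings needs stating.

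The effect on the result cannot be quantified from the documents and may be nil. The conclusion rests on two things: the plan's own expectation that patients will probably recognise the scent (expected, not certain), and the inference that patients mark the VAS. It should be corrected before the trial is reported, but it gives no reason to change the endpoint, sample size or analysis.

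**What to change.** 1. **Correct the description.** Replace the blinding statements in Specific Aims, Rationale and Overview, and Study Sample with wording such as: *Allocation is concealed by coded vessels. Patients, the delivering investigator and the observer are not told the assignment. Patients and the delivering investigator may recognise the scent.* Do not report the trial as double-blind. State in the conclusion that a difference on the patient-marked VAS could partly reflect expectation.
2. **Specify the observer's role.** State that the already planned observer, who was not present during inhalation, collects both the 30- and 60-minute VAS after the oil is removed. Note that some odour may remain at 30 minutes.
3. **Optional.** After the last VAS, ask which oil the patient believes was under test (rose, almond, do not know) and report the answers descriptively by arm only. An answer given then may reflect pain relief already felt, so it cannot size a bias. If the consent form names the control, the question adds little.

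The cost is a wording amendment, loss of the double-blind label, the observer's time at a second reading if only one was intended, and one short question if the optional item is adopted.

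### Section E compares the arms on raw VAS change without adjusting for baseline VAS: valid on average, but less precise and exposed to chance baseline imbalance with 30 per arm

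*Combined protocol and SAP*

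**What the plan says.** Section D (Rationale and Overview) provides a baseline value and two later ones: "A VAS pain scale will be recorded before treatment, after 30 minutes of treatment, and after a following 2nd 30 minutes". Section E states that the differences "will be aggregated from their respective 100 mm VAS for pain and the change calculated for each patient". It then names the test: "One-tailed paired t-Tests will be then conducted on the means after standard deviation is calculated and compared between treatment and control groups". Section A sets the target as a "significant change in VAS score greater than 13 mm between both groups".

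The pre-treatment VAS has no role except as the value subtracted. No covariate, regression model or stratification by starting pain is named. Section D (Study Sample) describes block randomization, 30 per arm, without stratification. On sample size it says "A sample size was calculated to be 30 patients for each treatment arm based on a power of 0.80" and "desired p value below 0.05". It gives no SD, and Section E mentions one only as something to be computed from the trial data ("after standard deviation is calculated").

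**The concern.** Subtracting the baseline assumes that each extra millimetre of starting pain carries through in full to the post-treatment reading. When the pre-post correlation is below 1 and the SDs are equal, less than a millimetre carries through, and subtraction over-corrects. The arm that happens to start higher then appears to improve more. With 30 per arm, chance baseline differences of several millimetres are ordinary, and the trial is looking for 13 mm.

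Two things are at stake. One is precision: the raw-change contrast has a larger variance than it needs. The other is how the single realized trial can be read: if the arms differ visibly at baseline, part of the reported difference will reflect that imbalance, and any adjustment chosen afterwards will look post hoc.

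**Working it through.** **Inputs from the documents.** 30 per arm, 1:1; power 0.80; p below 0.05; one-tailed test (Section E); 13 mm difference (Section A). The sample-size sentence does not name the 13 mm, so using it there is an assumption.

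**Assumptions.** VAS SD S = 20 mm at baseline and after treatment; pre-post correlation r = 0.3, 0.5 or 0.7, extended to 0.8 and 0.9. Section E's test is read as a comparison between arms.

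**1. The plan's own figure.** Without an SD, the 30 per arm cannot be reproduced. Solving for the SD of the analysed variable, with no loss:

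- one-sided: 13 x sqrt(30/2) / (1.645 + 0.842) = 20.2 mm
- two-sided: 13 x sqrt(30/2) / (1.960 + 0.842) = 18.0 mm

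With S = 20 and r = 0.5 the SD of change is 20.0 mm, so the middle case below matches the stated size under a one-sided test.

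**2. Chance imbalance and its carry-over.** The SE of the baseline difference is 20 x sqrt(2/30) = 5.16 mm; 1.96 SE is 10.1 mm. The shift in the raw-change contrast is (1 - r) x imbalance, in favour of the arm that starts higher.

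| r | 1-SE imbalance | 1.96-SE imbalance |
|---|---|---|
| 0.3 | 0.7 x 5.16 = 3.6 mm | 7.1 mm |
| 0.5 | 0.5 x 5.16 = 2.6 mm | 5.1 mm |
| 0.7 | 0.3 x 5.16 = 1.5 mm | 3.0 mm |
| 0.8 | 0.2 x 5.16 = 1.0 mm | 2.0 mm |
| 0.9 | 0.1 x 5.16 = 0.5 mm | 1.0 mm |

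**3. Precision.** Var(change) = 2S²(1 - r); Var(ANCOVA) = S²(1 - r²); ratio = (1 + r)/2. The variance therefore falls by 35%, 25%, 15%, 10% and 5% at r = 0.3, 0.5, 0.7, 0.8 and 0.9. One-sided power is Φ(13 / (SD x sqrt(2/30)) - 1.645).

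| r | SD, change | SD, ANCOVA | Power, change | Power, ANCOVA | n per arm for 0.80 (change, ANCOVA) |
|---|---|---|---|---|---|
| 0.3 | 23.7 | 19.1 | 0.69 | 0.84 | 41, 27 |
| 0.5 | 20.0 | 17.3 | 0.81 | 0.90 | 30, 22 |
| 0.7 | 15.5 | 14.3 | 0.95 | 0.97 | 18, 15 |

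Two-sided, the powers are 0.57 to 0.75, 0.71 to 0.83 and 0.90 to 0.94.

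**4. Sensitivity to S.** At r = 0.3, 0.5 and 0.7, the 1.96-SE carry-over is 5.3, 3.8 and 2.3 mm for S = 15, and 8.9, 6.3 and 3.8 mm for S = 25. For S = 25, one-sided power rises from 0.52 to 0.68, 0.64 to 0.75 and 0.83 to 0.88.

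**5. Check for systematic bias.** 20,000 null trials were simulated at each of r = 0.5 and 0.7, with 30 per arm, a milder-pain entry filter and a 10 mm fall in both arms. The mean raw-change contrast was -0.02 mm and one-sided type I error was 0.050. In trials where rose started more than 1 SE higher, raw change showed a mean spurious benefit of 3.3 mm (r = 0.5) or 1.9 mm (r = 0.7); ANCOVA showed 0.1 mm.

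**The case against.** The strongest reply is that an unadjusted comparison of change is valid. Its standard error already allows for chance baseline differences, and the error rate is right. This stands: the point concerns efficiency and the reading of one realized trial.

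The size of the gain can also be disputed, with reason. The SD and correlation are assumptions. At r = 0.5 and one-sided testing, raw change already reaches 0.81, so the planned 0.80 is met. The readings come only 30 and 60 minutes after baseline, so a correlation above 0.7 is possible; at 0.8 or 0.9 the variance saving is only 10% or 5%. The 7.1, 5.1 and 3.0 mm figures lie at the edge of the 95% range of imbalance and are not typical.

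A reader might infer more than the documents support:

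- **That the entry filter creates the imbalance.** Patients are approached when the physician "does not anticipate immediate need for narcotic pain medication". That judgement precedes allocation and is common to both arms, so it cannot make them differ. If it narrows the baseline range, it makes imbalance smaller: the SD of the baseline difference was 4.1 mm in the filtered simulation, against 5.2 mm unfiltered.
- **That spontaneous recovery or regression to the mean biases the contrast.** The documents do not say that pain falls on its own over the hour. If it does, it acts on both arms and cancels on average. It would count as effect only if the test called paired were run within each arm, which is a separate point about naming the test.
- **That a floor at 0 supports adjustment.** In a simulation with an assumed baseline mean of 35 mm, the 13 mm effect shrank to 10.7 mm under both analyses, so ANCOVA does not restore it. The inclusion criteria are an attachment that is not reproduced, so a minimum entry VAS may exist.

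**Conclusion.** The concern holds as one of lost precision and of error conditional on chance imbalance. It does not show systematic bias or an inflated error rate.

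The direction needs only a pre-post correlation below 1 with similar SDs before and after. The size depends on the assumed SD and correlation. With S = 20 mm, adjustment matters most at a correlation of 0.3, where 30 per arm falls short of 0.80 power on raw change but exceeds it with ANCOVA. It matters little at 0.8 or above. Since the plan states neither quantity, it cannot show that it is in the favourable range.

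**What to change.** In Section E, replace the t-test on raw change with a linear model of post-treatment VAS containing arm and pre-treatment VAS (ANCOVA), fitted separately at 30 and at 60 minutes. Report the adjusted rose-almond difference with its confidence interval. Keep raw change by arm as a descriptive summary, and report baseline VAS by arm. Specify this before any outcome is seen by arm, so that adjustment does not depend on the imbalance observed.

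The cost is a sentence or two in Section E. The baseline VAS is already collected, so no extra patients, visits or measurements are needed. Naming this model also removes the ambiguity of a paired test for two independent arms.

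### The only VAS test named is a paired t-test, but rose and almond patients are independent groups; an independent between-arm test should be named

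*Combined protocol and SAP*

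**What the plan says.** - **Comparison.** Section A sets out "the use of Rosa damascena essential oil versus a control of Almond Oil" and states: "Our primary endpoint will be the evaluation of significant change in VAS score greater than 13 mm between both groups".
- **Design.** Section D, Rationale and Overview: "Patients will be treated with either Almond Oil extract or Rosa damascena extract". Under Study Sample, "30 treatments will be distributed to each arm" by block randomization. No crossover or matching is described.
- **Measurement.** Section D, Rationale and Overview: "A VAS pain scale will be recorded before treatment, after 30 minutes of treatment, and after a following 2nd 30 minutes".
- **Test.** Section E computes a change for each patient and continues: "One-tailed paired t-Tests will be then conducted on the means after standard deviation is calculated and compared between treatment and control groups". No other test is named for VAS. The chi-squared test covers satisfaction and subjective pain reports, and a further t-test covers rescue medication.
- **Levels.** Study Sample gives 30 per arm, power 0.80 and "desired p value below 0.05, and 95% confidence intervals", and allows for losses ("with the anticipated possibility of patient loss or desire to withdraw during treatment") without a rate. No SD is given.

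**The concern.** A paired t-test needs two measurements on the same or a matched unit. The only pairs in this trial are the pre- and post-treatment scores of one patient. The primary endpoint is a contrast between two separate groups of patients, so the named test and the question do not fit. The sentence can be read in three ways:

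- **(a)** A pre/post paired test within each arm, with the two results then compared. Each test asks whether pain fell in that arm; neither asks whether it fell more with rose.
- **(b)** Per-patient changes compared between arms. This answers the question, but it is an independent-samples test under the wrong name.
- **(c)** Rose patients paired with almond patients. The design gives no basis for such pairs.

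At stake is the primary conclusion. Under (a), equal oils can look different and a real advantage can be hidden, depending on how much pain falls with almond, which is unknown. Leaving the reading open also leaves the choice of primary analysis until data are in hand.

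**Working it through.** **Inputs.** From the protocol: 30 per arm, 0.05, one tail, 13 mm. Assumed, because the documents give no value: SD of change 20, 25 or 30 mm, the same in both arms; the mean fall with almond; 24 completers per arm as an example of loss. Triplets below follow that SD order.

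**The plan's own figure.** The 30 per arm cannot be reproduced forward without an SD. Solved backward for 80% power at 13 mm, one-tailed (noncentral t), it implies an SD of about 20.0 mm for an independent test, or 28.0 mm for a within-arm paired test. It therefore does not reveal which test was planned.

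**Building blocks.**
- Within-arm paired test, mean fall m: noncentrality m√30/SD, 29 df. For m = 13: 3.56 / 2.85 / 2.37, so power p = 0.966 / 0.872 / 0.749.
- Independent test, difference 13 mm: noncentrality 13/(SD√(2/30)), 58 df: 2.52 / 2.01 / 1.68, so power = 0.800 / 0.635 / 0.506.

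**Reading (a), equal oils.** The arms are independent, so the chance that rose is significant and almond is not ('rose only') is p(1 − p).
- Both fall 13 mm: 0.966 × 0.034 = 0.033; 0.872 × 0.128 = 0.112; 0.749 × 0.251 = 0.188.
- Neither falls: 0.05 × 0.95 = 0.0475.
- Maximum, at p = 0.5: 0.25, reached at common falls of 6.2 / 7.7 / 9.2 mm.
- Simulation of 200,000 trials per case at 13 mm gave 0.032 / 0.112 / 0.187, with the independent test rejecting in 0.050 / 0.050 / 0.049.

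**Reading (a), rose truly 13 mm better.** 'Rose only' = p_rose(1 − p_almond). For example, at SD 20 with almond at 0 mm: 0.966 × 0.95 = 0.918.

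| Fall with almond | SD 20 | SD 25 | SD 30 |
|---|---|---|---|
| 0 mm | 92% | 83% | 71% |
| 5 mm | 62% | 71% | 73% |
| 8 mm | 31% | 47% | 58% |
| 13 mm | 3% | 13% | 25% |
| Independent test, any almond fall | 80% | 64% | 51% |

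**Losses.** With 24 completers per arm, independent power is 72 / 55 / 43%, and 'rose only' for equal 13 mm falls is 7 / 16 / 22%.

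**Reading (b).** No numerical error; only the label is wrong.

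**Reading (c).** With pairs fixed blind to outcome, degrees of freedom fall from 58 to 29 and power at SD 20 from 0.800 to 0.792, with type I error unchanged. The cost is small, but the p-value depends on an arbitrary order and completers without a partner are dropped.

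**The case against.** The strongest reply is that the intent is clear. The sentence itself ends with a comparison between groups, the preceding one computes a change per patient, and the endpoint is a between-group change. All three point to reading (b), where nothing goes wrong numerically. No passage states a rule that rose wins if it is significant and almond is not. Comparing the mean changes by means of their SDs would also be a valid contrast, merely an unnamed one. Further, if the endpoint requires an observed between-arm difference above 13 mm, 'rose only' together with that condition occurs for equal oils in only 0.6 / 2.2 / 4.4% of trials even at the worst common fall.

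Much of this is fair. A between-arm comparison is plainly wanted, and the 'rose only' figures apply only under reading (a). But intent does not supply a test. The one VAS test named is paired, while the same section describes the rescue-medication t-test as between groups without that word, so a literal analyst has reason to run pre/post tests. The 13 mm condition is one possible reading of section A and does not appear in section E.

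Two related points stand but are separate. If the observed difference must exceed 13 mm, power at a true 13 mm is about 50 / 50 / 48%. And a one-tailed 0.05 test beside a two-sided 95% interval can disagree: at a true 13 mm, about 10 / 13 / 13% of trials would be significant with an interval that includes zero. Both come from choices already in the protocol.

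**Conclusion.** The concern holds. For the primary comparison, the named test is either wrong (reading a) or misnamed (reading b), and no other section resolves it. That conclusion follows from the design and depends on none of the assumed numbers.

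The size of the harm does depend on them, and arises under reading (a). There the false pattern for equal oils ranges from below the nominal 5% to 25%, and the chance of showing a real advantage depends on the unknown almond response. Because this is the primary analysis, it should be corrected before data are analysed.

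**What to change.** Replace the t-test sentence in section E with wording such as:

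> At each stated time (end of the 30-minute treatment, and 30 minutes later), the per-patient change in VAS from baseline will be compared between arms with a one-tailed independent-samples t-test at 0.05 (alternative: larger fall with rose oil). The between-arm mean difference will be reported with its 95% confidence interval. Within-arm changes are descriptive only.

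The direction of the tail is not written in the protocol. It is inferred from almond being the control, and the investigators should confirm it. The one-tailed choice, both time points, the 0.05 and 95% levels and the role of the 13 mm threshold are left as they stand, for separate decision.

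An optional improvement, not needed for validity, is to replace the t-test with ANCOVA of post-treatment VAS on arm and baseline VAS. With equal variances and baseline correlation r, its residual variance is (1 + r)/2 times that of the change score. At an assumed SD of change of 20 mm the effective SD is 16.1 / 17.3 / 18.4 mm for r = 0.3 / 0.5 / 0.7, and one-tailed power is about 0.93 / 0.89 / 0.85 against 0.80 (57 df).

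Cost: one sentence. Baseline VAS is already collected; no new data, staff or patients are needed, and the sample size is unchanged.
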